		
T-score ≤ -2.5 at total hip, femoral neck, lumbar spine, or distal radius scan at screening visit.
 
FRAX 10-year risk scores $\geq 3\%$ for hip fracture or $\geq 20\%$ for major osteoporotic fracture (TBS adjusted FRAX is preferable if available).
 
Chronic back/shoulder/knee pain with current or past (within 1 year) prescription medication use for at least 3 months.
 
Severe, diagnosed arthritis (osteoarthritis, rheumatoid arthritis, or gout) with current or past (within 1 year) prescription medication use for at least 3 months.
 
Past (ever) or planned (next 12 months) back surgery.
 
Past (6 months prior) or planned (next 12 months) joint replacement surgery.
 
Past (ever) unilateral or bilateral hip replacement surgery, or metal device or fixation in hip, pelvis or femur.
	
Co-morbidity/health status	Approved for participation by Study Coordinator	
Uncontrolled hypertension (BP$>160/90$ mmHg)
 
Current or recent past (within 1 year): severe symptomatic heart disease, uncontrolled angina, stroke, chronic respiratory disease requiring oxygen, neurological or hematological disease requiring treatment for at least 3 months in past year; cancer requiring treatment in the past year (except non-melanoma skin cancer).
 
Low vitamin D (<20 ng/mL), abnormal kidney or liver function (2x upper limit of normal), eGFR<45 mL/min/1.73 m², Anemia (Hb< 13 g/dL in men/< 12 g/dL in women); Uncontrolled diabetes (fasting glucose >140 mg/dL)
	
BP measurement
 
Self-report on Medical History Form
 
Metabolic panel
 
CBC screening blood test

Medication use		Use of growth hormones, weight loss medications, oral steroids, insulin, , or prescription osteoporosis medications in the past year (see medication list).	Self-report on Medical History Form
Technology Status	Willing to complete online/electronic study forms and participate in virtual group sessions, as needed	No home computer, laptop, or tablet with reliable home internet OR no smartphone (touch-screen enabled phone) with reliable unlimited mobile internet.	Self-report

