Research participation	
Willing to provide informed consent; agree to all study procedures and assessments;
 
Able to provide own transit to assessment/intervention visits
	
Involved in another behavioral/interventional research study, weight loss program or undergoing physical therapy; Unable to tolerate diet, vest, or CT scan (claustrophobia).
 
Judged unsuitable for the trial for any reason by clinic staff
	Self-report

Schedule of assessment visits

Those who pass phone screening will be scheduled for a screening visit (SV1) which is conducted in the early morning following a 10 hour fast. Before any data collection, participants provide written informed consent and complete a HIPAA authorization form in accordance with our IRB policy. At this visit, weight and height will be measured to calculate BMI. Individuals who meet the BMI criteria will be queried on demographic information and medical history, undergo medical assessments including a blood pressure and

pulse check, comprehensive review of medications, and a fasting blood draw (comprehensive metabolic panel and complete blood count); the Center for Epidemiologic Studies Depression Scale (CES-D)⁶⁶ and the Montreal Cognitive Assessment (MoCA)⁶⁶ to ensure participants are not depressed and do not have impaired cognitive function (MoCA score ≥ 20). Individuals with clinically abnormal results at screening will be referred to their primary care providers with their permission.

Potential participants will also be familiarized with the resistance training protocol and asked to complete a dietary and VEST run-in to determine their ability to comply with the intervention protocols. For the dietary run-in, all participants will be provided with and oriented to the OPTAVIA® Optimal Weight 4 & 2 & 1 Plan® guide, sample meal plans, 3 one-day dietary trackers, a sampling of 12 OPTAVIA “Fuelings” (meal replacement products), 3 one-day Product Satisfaction Forms, asked to follow the OPTAVIA Optimal Weight 4 & 2 & 1 Plan for a three day period occurring over the following week, and report on their willingness to follow the diet plan. For the VEST run-in, participants will be asked to wear an unloaded vest for 3 days, and report on their willingness to wear the vest for 8 hours/day for 12 months, if randomized to that arm (SV2).

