Eligible participants will undergo further testing at two additional screening visits (SV2, SV3) prior to randomization (using a web-based system, stratified by sex with random block sizes) and intervention start, with outcome assessments repeated at 6 and 12 month testing sessions (see **Table 3** for a detailed assessment timeline). Briefly, outcome measure assessments include: anthropometric measures, physical function testing (grip strength, leg strength, walking tests, stair climb), resting metabolic rate, accelerometry, imaging (DXA and CT), self-reported fatigue, fatigability, and pain, physical activity, and self-efficacy, and blood storage.

Following state and institutional guidelines, modifications to screening and assessment visits will occur initially, and be conducted with as limited participant contact as possible, to ensure the safety of staff and participants, and to decrease the risk of exposure to COVID-19. Modifications will include dividing SV1 into two separate visits: SV1 and SV1-A. Those who pass SV1, will be scheduled for a remote screening visit (SV1-A) to be conducted by phone. At this remote visit, individuals will be queried on medical history, comprehensive review of medications, physical activity status, and the Center for Epidemiological Studies Depression Scale (CES-D). Additional modifications to assessment visits (SV3, FV2, and FV4) and intervention (INT) will include the administration of certain questionnaires and surveys by phone (see **Table 3** for specific questionnaires and surveys). When permissible by the state and the institution, in-person contact for visits will resume following necessary guidelines. Visits will revert back to the original protocol as described above and in **Table 3**, and these changes will no longer be in effect.

Study Interventions

Contact frequency and goals of each component of the three treatment groups for the intensive WL phase (Months 1-6) and the reduced contact WL phase (Months 7-12) are summarized in **Table 1** above.

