Phone Screener	x											
Informed consent/HIPAA		x										
Demographics		x										
Medical history		x	x									
Medications		x	x	x	x		x	x		x	x	x
Depression (CES-D)		x	x				x			x		x
Cognitive Assessment (MoCA)		x								x		
Pittsburgh Fatigability Scale					x		x			x		x
PROMIS Pain Intensity and Fatigue					x		x			x		x
CHAMPS physical activity		x	x				x			x		x
Adverse Events				x	x	x	x	x	x	x	x	x
Physical Exams and Physical Performance Measures												
Vital signs (ht/wt/bp/pulse)		x		x	x		x	x		x	x	
Anthropometric Measures				x			x			x		
eSPPB				x			x			x		
Hand Grip Test				x			x			x		
RMR					x			x			x	
Activity Monitor - thigh				x			x			x		
Activity Monitor - in vest						x			x			
400 meter Walk – fast				x			x			x		
TUG				x			x			x		
Biodex					x				x		x	
Stair climb				x			x			x		
Radiology/Imaging Tests												
DXA (whole body, hip, spine, forearm)				x			x			x		
CT (hip and spine)					x			x			x	
Phlebotomy												
CBC		x										
Metabolic Panel		x										
Vitamin D					x							
Plasma/Serum Storage					x				x		x	
Other												
D3-Creatine muscle mass (dose/collection)				x	x					x	x	
Run-in instructions		x		x								
Participant Satisfaction									x			x
Self-Efficacy						x			x			x
Adherence monitoring (weight, dietary trackers, meet with study dietitian as needed)						x			x			

Table 3. Proposed Assessment Timeline.

PS=phone screen, SV=screening visit, FV=follow up visit, INT=intervention; eSPPB =expanded short physical performance battery, RMR=resting metabolic rate, TUG=timed up and go, DXA=dual energy x-ray absorptiometry, CT=computed tomography, CBC=complete blood count.

Study Measure(s)

Methods for Primary Outcome Measure Assessment. Our study is powered to detect group differences in our primary outcome of 12 month change in total hip trabecular vBMD measured from CT scans acquired at baseline and 12-month follow-up visits. CT scans will also be acquired at a 6-month visit to assess changes in the outcomes at the end of the intensive WL phase. For completeness, below we describe the CT scanning protocol and vBMD image acquisition and assessment methods for the total hip, femoral neck, and lumbar spine regions of interest.

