CT Scanning Protocol. A helical CT scan including the femurs and lumbar spine will be obtained at baseline, 6, and 12 months on a 64-slice scanner (PET/CT GE Discovery MI scanner housed within the WFSM Translational Imaging Program). Scans will be acquired with SFOV 50 cm and 120 kV with standard reconstruction and secondary reconstruction using a bone algorithm. The scan will cover from the top of L1 through 3 cm below the mid-shaft of the femurs (mid-shaft defined as the midpoint between the superior aspect of the greater trochanter and the inferior aspect of the lateral condyle). The 5-port bone mineral calibration phantom (Mindways CT, Austin, TX) will be imaged in every scan and must be positioned to cover the lumbar spine through the lesser trochanter. In rare instances where the calibration phantom does not properly cover these regions, a scan may need to be repeated for proper data collection. The repeat scan will add approximately 975 millirem of radiation or less to the participant's radiation dose. Participants will have the option to decline a repeat scan, if it is determined that one is needed. In an effort to avoid repeated scans, trained study staff are present at each scan to ensure that the CT protocol is administered correctly. However, there may be times where study staff are not able to be present, and a re-scan may be needed if the scan is not acquired properly during these instances. Quality assurance of the CT system will be performed according to manufacturer specifications.

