Biomarkers of Bone Turnover and Key Regulators of Bone Metabolism. Blood samples will be collected in the morning via venipuncture after an overnight fast (of ≥10 hours) and abstinence from physical activity for the previous 24 hours for later analyses of bone turnover and other biomarkers. Aliquots of plasma and serum will be stored at -70°C in the Gerontology BioRepository directed by [name] until use in future assays.

D3-Creatine (D3Cr) muscle mass: Participants will be asked to ingest a small tablet containing 30 mg of D3-creatine, prepared by Wellspring Compounding Pharmacy (Berkeley, CA) to allow for a direct measure of muscle mass. 115 Participants will be given the dose at the SV2 and FV3 visits, and instructed to take the dose 3-6 days prior to their SV3 and FV4 visits (respectively) where they will be asked to provide a fasted urine sample. Urine will be collected either in a specimen cup and aliquoted, or will be collected directly on a filter paper strip, which will be frozen until shipment to the central lab at the University of California, Berkeley for detection of labeled and unlabeled creatinine by LC/MS.

Descriptive Data, Potential Covariates, and Adverse Events. Covariate assessment will occur at the frequency described in **Table 3**. Briefly, baseline demographic data will be recorded based on participant self-report (at baseline only). Medical information on prior and existing co-morbidities and hospitalizations will also be ascertained by self-report. Collectively, this information will be used to assess 10 year major osteoporotic and hip fracture risk using the FRAX tool.¹⁰⁴ We will also record medication use by asking participants to bring in all medications (including nutritional supplements). Height without shoes will be measured to the nearest 0.1 centimeter using a stadiometer and body mass will be measured to the nearest 0.1 kilogram using a calibrated and certified balance beam scale. Height and body mass will be used to calculate body mass index (BMI). Waist circumference will be measured to the nearest 0.1 cm with a Gulick-II spring-retractable steel tape. Resting metabolic rate (RMR) will be measured in the morning after an overnight fast by indirect calorimetry. Upon arrival, participants are asked to lie quietly for 15-20 minutes before testing. Measurement of oxygen consumption and carbon dioxide production are collected continuously for at least 30 minutes and RMR is

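### Low vitamin D is an exclusion, but its only scheduled draw is at the baseline CT visit and nothing requires the result before the scan

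*Combined protocol and SAP*

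**What the plan says.** Four places in the combined protocol and SAP bear on this point.

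- **Table 2, co-morbidity/health status row.** The exclusions include "Low vitamin D (<20 ng/mL), abnormal kidney or liver function", followed by eGFR, anemia and fasting glucose limits. For blood tests, the Assessment column names a metabolic panel and a "CBC screening blood test". It names no vitamin D assay and no visit for one.
- **Schedule of assessment visits, SV1.** The visit includes "a fasting blood draw (comprehensive metabolic panel and complete blood count"). Vitamin D is not listed.
- **Schedule of assessment visits, after SV1.** "Eligible participants will undergo further testing at two additional screening visits (SV2, SV3) prior to randomization".
- **Table 3.** The "Metabolic Panel" and CBC rows are marked at SV1 only. Vitamin D has its own row, marked at SV3 only. The row "CT (hip and spine") is marked at SV3, FV2 and FV4.

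On radiation, the CT Scanning Protocol says of a rescan: "The repeat scan will add approximately 975 millirem of radiation or less". The assessment-risk section gives 1866 millirem for all DXA and CT procedures, against an annual background of 300 millirem.

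**The concern.** An exclusion that depends on a blood test is best settled before a participant is exposed to radiation on the trial's behalf. Here the only vitamin D draw and the first CT share a visit, and the plan does not say which result or procedure comes first. If the scan is done before the result is read, a person below the threshold has had a CT that can serve no trial outcome.

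That person would also have completed other SV3 baseline tests and been told to take the D3-creatine tablet in the days before the visit. What is at stake is avoidable exposure and wasted baseline work. No hypothesis, estimate or power figure depends on it.

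**Working it through.** The check is mainly one of visit order. The arithmetic concerns only the size of the exposure.

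**1. Where each exclusion test falls.** The visit columns of Table 3 run PS, SV1, SV1-A, SV2, SV3, INT, FV1, FV2, INT, FV3, FV4, and a final phone column. Matching marks to columns gives:

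| Test | Visit(s) marked |
|---|---|
| CBC | SV1 |
| Metabolic panel | SV1 |
| DXA (T-score exclusion) | SV2, FV1, FV3 |
| Vitamin D | SV3 |
| CT | SV3, FV2, FV4 |

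Vitamin D is thus the only blood-test exclusion drawn at the CT visit. The others are drawn at SV1, and the DXA exclusion is assessed at SV2. Table 3 shows no blood draw at SV2, so SV1 is the only draw that precedes SV3.

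**2. Is the SV3 column read correctly?** The D3-creatine row reads SV2, SV3, FV3, FV4. The methods text agrees: "Participants will be given the dose at the SV2 and FV3 visits, and instructed to take the dose 3-6 days prior to their SV3 and" (the remaining visit named there is FV4). Urine is collected at SV3 and at FV4. That confirms the SV3 column. The SV1 text independently shows that vitamin D is not in the SV1 draw, although it cannot by itself distinguish SV2 from SV3.

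**3. Is the result required before the scan?** No section sets the order of procedures within SV3, states the assay turnaround, divides SV3 into separate days, or makes the CT conditional on the vitamin D result.

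**4. Dose of one scan.** The document's own multiples reproduce:

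- 1866 / 300 = 6.22
- 1866 + 975 = 2841
- 2841 / 300 = 9.47

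Let C be the dose of each scheduled CT, assumed equal across the three, and D the total DXA dose. Then 3C + D = 1866, so C = (1866 − D) / 3 ≤ 1866 / 3 = 622 millirem. Against background, 622 / 300 = 2.07 years.

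The 975 millirem figure cannot be the dose of every scheduled scan, since 3 × 975 = 2925, which exceeds 1866. It is worded as an upper limit and refers to a repeat scan.

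**5. Number affected.** This needs the proportion of people reaching SV3 with a value below 20 ng/mL, and the proportion of those scanned before the result is read. The document gives neither, so no count is offered.

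**The case against.** The strongest reply is that screening is staged by design. SV2 and SV3 are themselves called screening visits, and the T-score exclusion depends on the SV2 DXA. The word eligible in the sentence about SV2 and SV3 therefore cannot mean that every criterion has been cleared, and a reader who finds a contradiction there reads too much into it. This stands, and the point does not rest on that word.

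A reader might also infer that everyone who fails on vitamin D has already been scanned. The documents do not support that. Blood could be drawn and the result read before the CT, or SV3 could span more than one day. Neither is stated and neither is excluded, so the claim must stay conditional.

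A reader might infer that ineligible people are randomized. They need not be: SV3 comes before randomization, so the criterion can still be applied in time.

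A reader might take 975 millirem, or about 3 background years, as the dose of the baseline scan. The stated total does not allow that figure for each scheduled scan.

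Table 3 also has marks that look odd. In the Biodex and Plasma/Serum Storage rows the mid-study mark sits under INT and not under FV2, so a displaced mark elsewhere is possible. The D3-creatine check supports the SV3 column, which limits this objection without removing it entirely.

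Finally, the plan discloses the radiation and rates the risk as slight. That is fair, but it describes the scans of the study as planned. It does not give a reason to scan someone who could have been excluded beforehand.

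**Conclusion.** The point holds in conditional form. As written, the schedule allows a person who will be excluded for low vitamin D to receive the baseline CT first, because the only draw is at the same visit and no rule puts the result ahead of the scan. The exposure is at most about 622 millirem per such person, roughly 2 years of the stated background. This assumes that the three scheduled scans deliver equal doses; any DXA share lowers it.

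The number of such people is unknown. The consequence is limited to avoidable radiation and unused baseline assessments. Enrolment, the primary analysis and power are unaffected. It is worth changing because the remedy is cheap.

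**What to change.** Reconcile Table 2, the SV1 paragraph under Schedule of assessment visits, and Table 3 so that the vitamin D result is available and reviewed before the baseline CT. One way is to add the assay to the fasting draw already taken at SV1. This would also settle the criterion before the D3-creatine tablet is issued at SV2. Another is to keep the draw later but state that the SV3 scan does not go ahead until the result has been reviewed. In either case, name the vitamin D assay in the Assessment column of Table 2.

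The SV1 route needs no new visit or additional draw. Its cost is that some assays will be run on people who fail screening for other reasons. Keeping the draw at SV3 avoids part of that cost, but needs a result in time for the scan or a separate scan day.

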We will use a three group randomized design in 150 older (60-85 years), obese (BMI=30-40 kg/m² or BMI= 27.0-<30 kg/m² plus one risk factor), men and women who will undergo a 12 month WL intervention to test our overall hypothesis that weighted vest use added to WL will better preserve bone health compared to WL alone and similarly to WL plus a structured RT intervention. All groups will receive the same WL intervention (caloric restriction targeting 10% WL and with adequate calcium, vitamin D, and protein intake), in accordance with national obesity treatment guidelines.⁶⁵ Thus, treatment groups are: WL alone (**WL**; n=50); WL plus weighted vest use (**WL+VEST**; targeting 8 hours/d, weight replacement titrated up to 10% WL; n=50); or, WL plus structured RT (**WL+RT**; targeting 3 sessions/week; n=50); **Table 1.** All outcome assessments occur at baseline, six, and 12 months.

Table 1. Proposed Intervention Components by Treatment Group.

Intervention Components	Intensive WL Phase (Months 1-6)	Reduced Contact WL Phase (Months 7-12)
Weight Loss (WL)	Weekly behavioral-based group sessions; 10% WL goal following national obesity treatment guidelines	Biweekly behavioral-based group sessions; 10% WL goal following national obesity treatment guidelines
WL + Weighted Vest (WL+VEST)	WL + 8 hours/day weighted vest use titrated weekly to adjust for achieved WL (up to 10% baseline weight)	WL + 8 hours/day weighted vest use titrated biweekly to adjust for achieved WL (up to 10% baseline weight)
WL + Resistance Training (WL+RT)	WL + 3 days/week progressive, structured RT	

Recruitment of study participants: Randomization of 150 participants will ensure at least 85% statistical power (with a conservative drop-out rate of ~15%; n=128 completed) to detect significance between group differences in our primary outcome (12 month total hip trabecular vBMD). We plan to recruit, screen and enroll during Years 1-3.5 of the study. We will target older adults who live in the area via media advertisements and mass mailings.

Participant screening and randomization

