Weight Loss Intervention (WL; provided to all groups). All participants will undergo a dietary WL intervention designed to elicit behavioral changes leading to decreased caloric intake sufficient to result in a 10% loss of initial body mass (10 kg for a 100 kg individual). This degree of WL is entirely feasible within this timeframe, and we have prior success in achieving this goal in older adults.⁶⁷⁻⁶⁹ The WL intervention includes the use of a partial meal replacement (MR) program, group nutrition education, state-of-the-art methods for promoting WL based on the group dynamics literature, social cognitive theory, and strategies that optimize self-regulation.⁷⁰⁻⁷² All participants will be asked to initially follow the OPTAVIA® Optimal Weight 4 & 2 & 1 Plan®. This is a portion-controlled, reduced calorie (1100-1300 calories/day) weight loss meal plan and includes consumption of a total of 4 OPTAVIA MRs, 2 self-prepared lean and green meals, and 1 Healthy Snack per day. Each of the OPTAVIA MRs contain ~ 90 -110 kcals, 10-15 g protein, are fortified with at least 20% of the daily value for 24 vitamins and minerals (including calcium and vitamin D), and contain GanadenBC30 probiotic cultures. All OPTAVIA MRs share a similar nutritional profile, allowing them to be used interchangeably, and will be shipped directly to participants. Participants will purchase and prepare ingredients for the foods for the lean and green meals on their own. Each lean and green meal will consist of 5-7 oz. lean protein, 3 servings of non-starchy vegetables and up to 2 servings of healthy fat. The healthy snack will consist of a self-selected serving

of fruit, dairy, or grain purchased by the participant, or one of OPTAVIA's portable, pre-portioned, ready-to-eat snacks can be used as a healthy snack. Participants will be guided by the study RD on their food purchasing and preparation of the other meals and will be encouraged to consume only what is approved from the menu.

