In addition to receiving dietary counseling, all participants will be asked to attend virtual or in-person behavioral counseling group sessions led by the RD. These sessions will be held weekly for the first 6 months and bi-weekly for the remainder of the study to provide participants an opportunity to review specific questions and problems. The education and counseling component of the intervention will emphasize instruction in making healthy, lower-calorie food choices while teaching changes in behavioral habits to promote WL and prevent weight regain.⁷³ Specific emphasis will be placed on the acquisition and use of self-management skills, particularly self-monitoring of diet and weight, and achieving 150 minutes of aerobic activity/week, in accordance with national guidelines.^{65,74} Throughout the 12 month WL phase, participants will be asked to track their food/beverage intake (including the number of meal replacements consumed each day) daily for the first three months and then on a reduced schedule as warranted. These will be reviewed routinely by the study registered dietitian. Body weight will be measured and recorded at all group sessions to provide additional feedback and to increase motivation. Official study weights will occur at SV3, FV2, and FV4. If it is evident (either through review of diet records or inadequate WL) that participants are struggling to meet their WL goals additional individual counseling sessions with the RD will be held to improve compliance. At FV1 and FV3, participants in this group will be asked to complete a program evaluation form to solicit feedback on overall WL program satisfaction, desired future usage, and product preferences. Periodically throughout intervention, participants will be asked to rate their confidence (i.e., self-efficacy) in meeting the demands of the intervention they are receiving. They will also be asked to report changes in their health and medication.

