Aim 2, Hypothesis 2. We anticipate that the change in total hip aBMD among the WL+VEST will be noninferior to the change among WL+RT. The noninferiority margin (i.e. difference at which a clinically meaningful increase of nonvertebral fracture risk may occur¹¹⁵) for the difference in 12 month total hip aBMD changes is -2.13% of baseline or -0.022 g/cm². Assuming equivalence between WL+VEST and WL+RT (i.e., WL+VEST and WL+RT 12 month mean are each 3% reduced from baseline (0.996 g/cm²) as used in Hypothesis 1), then a baseline sample size of 50/group provides 80% power to establish noninferiority of WL+VEST compared to WL+RT such that the lower bound of the one-sided 0.9875 confidence bound of the group mean differences will be greater than a -0.022 g/cm² difference between WL+VEST minus WL+RT. This assumes 1) the same common group SD of change (0.033 g/cm²) as in Hypothesis 1; 2) attrition rate is 15%; and 3) the Type I error rate is 0.0125, based on the convention of using 0.025 for a one-sided confidence interval, which is further divided in half due to having co-primary hypotheses.

Aim 2, All other outcomes. Due to the challenges of prespecifying noninferiority boundaries for exploratory outcomes, all other analyses for the second aim will focus on the three group comparisons of WL, WL+VEST, and WL+RT. Based on the same baseline sample size of 50/group (n=150 overall), we will have 80% power to detect a relatively modest effect sizes (variance of means/within-group variance) of 0.116 under the attrition rate of 15% assumed above, assuming 2-tailed F-test and a 0.05 Type I error rate.

Statistical Analysis Plan. The primary aim for comparisons of total hip trabecular vBMD will be tested using a mixed model fit using the change in total hip trabecular vBMD at 12 months versus the treatment effect indicator for each of the three groups, adjusted for visit (6 or 12 months), visit by treatment interaction, sex (to account for randomization strata) and baseline value. A contrast statement will test change in total hip trabecular vBMD at 12 months in WL versus WL+VEST, and a statistically significant difference will be

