Safety measures during the interventions: For the dietary intervention, all study participants are monitored for compliance to a safe level of caloric deficit. Since the degree of bone and muscle loss is accelerated by the rate of weight loss, all participants will be weighed weekly and if weight is being lost at a rate greater than 0.9 kg/wk (~2 lb/wk), adjustments may be made to the meal plan to increase the level of calories recommended to slow down this excess rate of weight loss. As stated previously, at the outset of all group sessions, participants will be queried regarding problems or health symptoms they may be experiencing with the vest. The interventionist will record the presence or absence of such symptoms and determine whether or not the problem requires medical attention and, if so, to determine whether or not the contact should be handled emergently or, in consultation with the study physician, by a scheduled appointment with the primary care provider. Supervised RT sessions are conducted at a central location and are supervised by trained interventionists who monitor potential adverse experiences and symptoms. On-site staff trained in advanced cardiac life support are available to deal with medical emergencies. Also, institutional and community EMS services will be activated if needed. Procedures to minimize musculoskeletal discomfort to the exercise include teaching proper warm-up and cool down activities and providing instruction on correct exercise techniques and fall safety. If for any reason the participant reports a fall or other injury, or chest pain, shortness of breath, or dizziness, during a supervised RT session, they will be referred to their doctor, or study staff will notify the participant's doctor or other health care provider with their permission. If at any point during a RT session, participants develop chest pain, shortness of breath, or dizziness, they will be instructed to stop exercise, and to contact the study staff if these symptoms persist or recur. We monitor blood pressure and heart rate before and after all supervised RT sessions. If an intervention-related injury or illness does occur, the study medical staff will be consulted according to the type of symptom reported. In some instances, it may be appropriate to reduce or to temporarily suspend the participant's weight loss, vest use, or RT goals. If the injury or symptoms do not resolve after an appropriate period of time, the participant will be referred to his/her primary care provider for further evaluation. The participant will be encouraged to follow the primary care provider's instructions regarding intervention compliance.

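### Baseline body weight, measured before randomisation and setting the kilogram weight-loss target and vest-load cap, is not a covariate in the primary model: a small missed efficiency, not an error

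*Combined protocol and SAP*

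**What the plan says.** - **Weight-loss target** (Study Interventions, Weight Loss Intervention): the diet aims at "decreased caloric intake sufficient to result in a 10% loss of initial body mass (10 kg for a 100 kg individual"). The percentage is the same for everyone; the kilograms are not.
- **Vest load** (Table 1): titrated "to adjust for achieved WL (up to 10% baseline weight"). The load follows the loss achieved, and baseline weight sets its ceiling.
- **Randomisation** (Schedule of assessment visits): "stratified by sex with random block sizes", with no other factor.
- **Primary model** (Statistical Analysis Plan): change in total hip trabecular vBMD by treatment, "adjusted for visit (6 or 12 months), visit by treatment interaction, sex (to account for randomization strata) and baseline value". Both co-primary contrasts come from this model, and Aim 2 repeats the analysis for total hip aBMD.
- **Weight data**: Table 3 schedules weight at SV1, SV2 and SV3, all before randomisation, and the Weight Loss Intervention section says "Official study weights will occur at SV3, FV2, and FV4".
- **Other covariates** (Descriptive Data, Potential Covariates, and Adverse Events): admitted only if unbalanced between arms and related to outcome, and then only in exploratory secondary analyses. Separately, the Statistical Analyses paragraph allows baseline predictors of attrition or compliance to enter through stratification or multiple imputation.

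**The concern.** The background text before Objectives names reduced mechanical loading as a likely contributor to bone loss during weight loss. The safety section adds: "Since the degree of bone and muscle loss is accelerated by the rate of weight loss", and states its threshold in kilograms per week. On that reasoning, someone asked to lose more kilograms may lose more bone. If so, baseline weight accounts for some of the between-person spread in 12-month change, and the primary model leaves that spread in its residual.

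The routes the plan leaves open for other covariates depend on what the data show: an observed imbalance, or a link with attrition or compliance. Neither can deliver a prespecified gain in precision for the co-primary tests. At stake is a modest amount of power for the superiority contrast, together with some discretion over covariates after the data are seen.

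**Working it through.** **Inputs from the plan** (Sample Size and Power; Table 4): 50 per arm, 15% attrition, so n = 42.5 per arm; SD of change 0.010 g/cm³, described as unadjusted; two-sided α = 0.025; difference 0.0075 g/cm³. Assumed 12-month losses are 0.0165 (WL), 0.009 (WL+VEST) and 0.009 (WL+RT, from 0.300 to 0.291).

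**Inputs assumed, because the documents give none**: mean baseline weight 85-95 kg, SD 12-16 kg, bone loss proportional to kilograms lost.

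**1. Reproduce the plan's figure.** SE = 0.010 × √(2/42.5) = 0.00217. Noncentrality = 0.0075/0.00217 = 3.46. A noncentral t with 83 degrees of freedom gives 87.8%, against 87.7% in Table 4. The other five cells of Table 4 also reproduce.

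**2. How far the kilogram target varies.** With assumed heights of 1.50-1.85 m and BMI 27-40, weight runs from 27 × 1.50² ≈ 61 kg to 40 × 1.85² ≈ 137 kg, and the 10% target from about 6 to 14 kg.

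**3. Variance explained by weight.** Under proportionality the slope of bone loss on baseline weight in an arm is that arm's mean loss divided by mean weight. One covariate fits one common slope, so the relevant loss is the three-arm mean: (0.0165 + 0.009 + 0.009)/3 = 0.0115. Then R² = [(0.0115/mean weight) × SD of weight/0.010]².
- Mean 95 kg, SD 12 kg: (0.145)² = 2.1%.
- Mean 85 kg, SD 16 kg: (0.216)² = 4.7%.
- Weight not prognostic: 0%.

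**4. Power with weight in the model.** The residual SD becomes 0.010 × √(1 − R²).

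| R² | Power, difference 0.0075 |
|---|---|
| 0 | 87.8% |
| 2.1% | 88.5% |
| 4.7% | about 89.4% |

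The lost degree of freedom changes these by about 0.01 percentage point. Setting the partial correlation directly gives the same picture: 88.1% at r = 0.1 and 89.1% at r = 0.2.

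**5. Noninferiority (one-sided α = 0.0125).** At the -0.012 margin, power is already about 99.9%, so there is nothing to gain. At the stricter -0.0075 margin the figures match those in step 4.

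**6. Validity of the model as written.** In 40,000 simulated trials with 42 per arm, leaving out a covariate correlated with outcome at r = 0.3 or r = 0.5 gave Type I error of 0.0247 and 0.0238 against a nominal 0.025, with no bias.

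**7. Chance imbalance.** One standard error of the difference in mean weight is 12 × √(2/42.5) = 2.6 kg to 16 × √(2/42.5) = 3.5 kg. Multiplied by the common slope (0.0115/95 = 0.000121 to 0.0115/85 = 0.000135 g/cm³ per kg), this shifts the contrast by about 0.0003-0.0005 g/cm³. That is 4-6% of 0.0075, or about 0.15-0.22 of the contrast's standard error.

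**The case against.** The strongest reply is that nothing needs repair. The relative target is the same for everyone, and the plan also expresses bone loss in percent. If bone responds to relative unloading, weight has no predictive value. The safety statement concerns the rate of weight loss, not baseline weight. Sex, already a stratum and a covariate, carries part of the variation in weight, and baseline vBMD may carry more. The power calculation uses an unadjusted SD and already clears the plan's 85%. The same remark could be made about other baseline variables.

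Most of this stands, and it limits the size of the point. It does not remove it: weight is the baseline variable that sets the kilogram target and the vest cap, it is already collected, and adjusting for it costs almost nothing.

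A reader might infer more than the documents support:

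- **That weight is an established predictor of the outcome.** No passage gives a correlation or says so.
- **That the omission biases the vest effect or inflates Type I error.** It does neither. Chance imbalance is already part of the standard error.
- **That adjustment could explain more than 10% of the variance and lift power above 91%.** Reaching an R² of 11.5% requires applying the WL arm's largest assumed loss (0.018) to every arm, with the lowest mean weight and the highest SD. In the 0.0075 scenario the arms' losses differ, and a common slope gives at most about 5%.
- **That the plan makes no use of such covariates.** It has conditional routes, though none into the prespecified primary model.

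**Conclusion.** The point holds as a missed efficiency of small and uncertain size. Adding baseline weight would raise power for WL+VEST versus WL in the 0.0075 scenario by between 0 and about 1.6 percentage points (87.8% to at most about 89.4%), before any discount for what sex and baseline vBMD already explain. This rests on proportionality between bone loss and kilograms lost, a mean weight of 85-95 kg and an SD of 12-16 kg, none of which the documents supply. If weight does not predict vBMD change, the gain is zero. The analysis as written remains valid and adequately powered on its own assumptions.

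**What to change.** Before unblinding, add SV3 body weight as a continuous covariate, beside sex and the baseline outcome, in the primary mixed model (both co-primary contrasts) and in the matching total hip aBMD model. Keep the currently written model as a named sensitivity analysis. Do not adjust for achieved weight loss or vest load: both arise after randomisation and may lie on the path from treatment to outcome.

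The cost is one term in the model statement and one degree of freedom. SV3 weight is scheduled for every participant before randomisation, so no new measurement is needed.
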